4.5.2 Guidelines for Dose Modifications

Subjects will be monitored continuously for AEs while on study therapy. Subjects will be instructed to notify their physician immediately for any and all AEs. The criteria presented in this section and Table 4.5.2-1 for dose modifications and delays for BMS-986158 are meant as general guidelines.

- Subjects will continue to receive therapy as long as they have not had disease progression or an AE requiring dose modification, as described below.
- Dose modifications, interruptions, or delays may occur in the setting of lower grade AEs and/or be more conservative than indicated in Table 4.5.2-1 based on the clinical judgment of the investigator, and in consultation with the Sponsor/Medical Monitor.
- For BMS-986158, dose reductions should be to the previous lower dose level, or to a dose level in between the previous dose level and the current dose level, after discussion between Sponsor/Medical Monitor. A decision to remain at the current dose level requires a discussion and an agreement between the investigator and the Sponsor/Medical Monitor.
- If several AEs of varying grade or severity occur simultaneously, the dose modification applied should be the greatest reduction applicable based on the worse grade (or severity) observed among the AEs reported.
- Assessment of causality (chronology, confounding factors such as disease, concomitant medications, diagnostic tests and previous experience with the agent) must be determined and documented by the investigator, prior to dose modification.
- If the same Grade 3 non-hematologic AE recurs despite a dose reduction, a second dose reduction versus discontinuation of the subject from further protocol therapy will be discussed and agreed upon by the Sponsor/Medical Monitor and investigators.
- Subjects who experience a Grade 4 non-hematologic AE will not receive additional protocolrelated therapy and will be removed from study unless discussed and agreed upon by the

Sponsor/Medical Monitor and investigators that it is in the best interest of the subject to receive additional therapy with BMS-986158 (for example, if the subject has demonstrated a response to therapy).

- No more than 2 dose level reductions of BMS-986158 will be allowed per subject. If a third dose reduction is required, the subject must discontinue BMS-986158 (and nivolumab, if receiving combination therapy based on response to therapy). Dose re-escalation after a dose reduction may occur in limited circumstances (such as a change in attribution of an AE, or if re-escalation is in the best interest of the subject) after discussion and agreement of the Sponsor/Medical Monitor and investigators. The number of dose modifications needed for a subject should be discussed and agreed between the investigator and the Sponsor/Medical Monitor.
- Skipped doses will not be administered within the same cycle.
- For an AE requiring dose modification, BMS-986158 (and nivolumab for subjects receiving combination therapy) should be interrupted to allow recovery from the AE. Re-initiation of study drug cannot occur until AE decreases to ≤ Grade 1 or baseline assessment. In case of delayed recovery to ≤ Grade 1 or baseline (except for alopecia) from treatment-related AEs that results in a delay of treatment for > 30 days, the subject will not receive additional protocol-related therapy and will be removed from study unless discussed and agreed upon by the Sponsor/Medical Monitor and investigators that it is in the best interest of the subject to receive additional therapy with BMS-986158 (for example, if the subject has demonstrated a response to therapy).
- For patients receiving combination therapy, if 1 study drug must be discontinued, the other study drug may be continued as single agent therapy based on discussion with Sponsor/Medical Monitor and the investigator.
- For subjects in Part 2 monotherapy expansion or (if pursued) combination expansion who report an AE requiring dose modification, the dose of BMS-986158 should be reduced from 3.75 mg to 3 mg. See Table 4.5.2-1.

For data collection and analysis purposes, all subjects will continue to be classified by the original treatment arm.

Table 4.5.2-1:DoseEven	Modification Criteria for BMS-986158 Drug-Related Adverse			
Adverse Event	Initial Action	Dose Modification		
Grade 4 febrile neutropenia	Discontinue BMS-986158	Discontinue BMS-986158		
Grade 3 febrile neutropenia	Hold BMS-986158 until return to baseline or Grade 1	1st event: Consider reduction by 1 dose level. 2nd event: Reduce by 1 dose level		
≥ Grade 4 hematologic toxicity (neutropenia or thrombocytopenia)	Hold BMS-986158 until returns to baseline or Grade 1.	1st event: Consider reduction by1 dose level.2nd event: Reduce by 1 dose level.		
Grade 3 thrombocytopenia with clinically significant bleeding	Hold BMS-986158 until return to baseline or Grade 1	1st event: Consider reduction by 1 dose level. 2nd event: Reduce by 1 dose level		
≥ Grade 3 non-hematologic AE in subjects receiving maximum medical management.	Hold BMS-986158 until resolves to baseline or Grade 1.	1st event: Consider reduction by 1 dose level.2nd event: Reduce by 1 dose level.		
QTcF > 500 msec confirmed by at least one repeat ECG	Discontinue BMS-986158	Discontinue BMS-986158		
≥ Grade 3 diarrhea not adequately controlled with medication at maximum doses	Hold BMS-986158 until resolves to baseline or Grade 1.	1st event: Consider reduction by 1 dose level.2nd event: Reduce by 1 dose level.		

T 11 4501 . . • . . .

If needed, based on the occurrence of DLTs or other AEs, an individual subject enrolled on any arm may have the BMS-986158 schedule revised to match the alternate schedule on an another arm, at the agreement of the investigator and Sponsor/Medical Monitor, in order to better manage the overall tolerability of study treatment. This schedule change may be in lieu of dose modification shown in Table 4.5.2-1. At the agreement of the investigator and Sponsor/Medical Monitor, subjects who have already had dose reduction may be restarted at the original dose under the revised schedule. For data collection and analysis purposes, all subjects will continue to be classified by the original treatment arm.

Reasons for dose modifications or delays, the supportive measures taken and the outcome must be documented in the subject's chart and recorded in the CRF.

Subjects will be monitored continuously for AEs while on study therapy. Subjects will be instructed to notify their physician immediately for any and all toxicity. The criteria presented in this section for dose modifications and delays are meant as general guidelines.

Assessment of causality (chronology, confounding factors such as disease, concomitant medications, diagnostic tests and previous experience with the agent) must be determined and documented by the investigator, prior to modifying any drugs.

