4.5.3 Management of Diarrhea for BMS-986158

For symptoms of diarrhea that occur at any time during treatment with BMS-986158, dose interruption is recommended until diarrhea resolves. After recovery, dose reduction or discontinuation should follow the criteria in Section 4.5.2 depending on the severity of the diarrhea. The following are guidelines for the management of diarrhea and are not intended to replace the clinical judgment of the treating physician(s):

For Grade 3 or higher events of diarrhea that are not controlled (ie, to Grade 1 or baseline) with loperamide or lomotil, dosing of BMS-986158 should be interrupted, as continued dosing will likely result in increased severity of diarrhea. In addition, evaluation of infectious causes should be considered. After recovery, dose reduction or discontinuation should follow the criteria in the protocol, depending on the severity of the diarrhea. The following are guidelines for the management of diarrhea, and should be used along with the clinical judgment of the treating physician(s).

- Diet: Recommendations should include eating small, frequent meals, diet modification (avoiding milk products, spicy and/or fatty foods, alcohol, and caffeine), and aggressive oral hydration.
- Treatment with Loperamide: Loperamide should be started at the earliest sign of (1) a poorly formed or loose stool, (2) the occurrence of 1 to 2 more bowel movements than usual in 1 day, or (3) an increase in stool volume or liquidity. Loperamide may be taken in the following manner: 4 mg at the first onset of diarrhea, then 2 mg every 2 hours around the clock until diarrhea-free for at least 12 hours. Subjects may take loperamide 4 mg every 4 hours during the night. This dose regimen is higher than the standard dose of loperamide but is typical for the treatment of diarrhea caused by anticancer therapy. Subjects should be provided with loperamide and instructed in its use at the initial treatment visit so that they have sufficient supply on hand in case antidiarrheal support is required. It is important that loperamide is taken as instructed. For subjects who cannot tolerate loperamide or who do not get adequate relief with maximum doses, standard doses of Lomotil® (diphenoxylate/atropine) may be added or used instead of loperamide.
- Additional antidiarrheal measures, such as octreotide, may be used at the discretion of the investigator or treating physician.

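### After a Grade 4 non-hematologic AE, the Section 4.5.2 bullet makes stopping BMS-986158 the default, but two rows of Table 4.5.2-1 that also reach Grade 4 say hold and reduce

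*Protocol*

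**What the plan says.** Protocol Section 4.5.2 has a list of bullets followed by Table 4.5.2-1.

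- **The bullet.** "Subjects who experience a Grade 4 non-hematologic AE will not receive additional protocolrelated therapy and will be removed from study unless discussed and agreed" by the sponsor's medical monitor and the investigators that continuing is in the subject's best interest. It is not limited to drug-related events.
- **The table.** It covers drug-related AEs. Two rows are written as at or above a grade: ≥ "Grade 3 non-hematologic AE in subjects receiving maximum medical management", and ≥ "Grade 3 diarrhea not adequately controlled with medication at maximum doses". Both give the same action: hold until baseline or Grade 1, consider one level down after the first event, and go one level down after the second.
- **Other rows do order a stop.** "Grade 4 febrile neutropenia" and "QTcF > 500 msec confirmed by at least one repeat ECG" both lead to discontinuation.
- **Section 4.5.3 on diarrhea.** It asks for interruption "For Grade 3 or higher events of diarrhea that are not controlled (ie, to Grade 1 or baseline) with loperamide or lomotil". It also says: "After recovery, dose reduction or discontinuation should follow the criteria in Section 4.5.2 depending on the severity of the diarrhea".
- **Section 3.5.** Discontinuations set out in Section 4.5.2 are mandatory. So is stopping when the investigator judges that an AE makes continued participation contrary to the subject's best interest.

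Section 4.5.2 twice describes its criteria as general guidelines.

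**The concern.** Both table rows include Grade 4, so a drug-related Grade 4 event that meets a row's qualifier falls under two instructions with different defaults. The bullet stops treatment unless continuation is jointly agreed. The row holds treatment and allows a restart. A site that reads only the table, which is the natural quick reference, could restart after a Grade 4 toxicity without the joint agreement that the bullet demands.

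The risk runs in one direction. A site that follows the bullet stays within the table, because Section 4.5.2 permits more conservative action in consultation with the sponsor. A site that follows the row alone can miss the bullet's condition. Since Section 3.5 makes the Section 4.5.2 discontinuations mandatory, the governing rule also decides whether that obligation applies.

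**Working it through.** The plan gives no figure to reproduce here. The check is a comparison of the texts, followed by a rough sizing.

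**1. Where the rules overlap.** The overlap needs all three of: drug-related (the table's scope), Grade 4 and non-hematologic (the bullet's scope), and one row qualifier (maximum medical management, or diarrhea uncontrolled at maximum doses). Outside it only the bullet applies and there is no conflict.

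**2. The instructions inside the overlap.**

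| Step | Section 4.5.2 bullet | Table 4.5.2-1 rows |
|---|---|---|
| Default | Stop | Hold |
| Condition for restarting | Joint agreement on best interest | Recovery to baseline or Grade 1 |
| Dose on restart | Not given | First event: consider one level down; second: one level down |

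**3. Is there a priority rule?**

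- The general-guidelines label covers bullets and table alike.
- The more-conservative clause is permissive.
- The instruction to apply the greatest reduction concerns several simultaneous AEs, not two rules for one AE.
- Sections 3.5 and 4.5.3 refer back to Section 4.5.2.
- Section 4.5.1 requires interruption for any AE meeting DLT criteria. That is the first step on either route, so it does not settle the default.

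None ranks the bullet against the table.

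**4. What intent can be inferred?** For diarrhea, Section 4.5.3 allows discontinuation according to severity. The diarrhea row contains no discontinuation. The other triggers in Section 4.5.2 that could reach diarrhea turn on recurrence, a third reduction or a delay beyond 30 days. The only one that turns on severity is the Grade 4 bullet, so Section 4.5.3 makes best sense if that bullet applies. A neighbouring bullet also adds to the table rather than repeating it: "If the same Grade 3 non-hematologic AE recurs despite a dose reduction, a second dose reduction versus discontinuation of the subject from further protocol therapy" is to be discussed and agreed. Both point to the bullet governing.

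**5. What can happen on the table route?** Staying at the same dose requires agreement with the sponsor's medical monitor. The number of dose modifications should be agreed with the sponsor. Restart before Grade 1 or baseline is barred. The investigator's best-interest stop in Section 3.5 still applies. What remains is mainly a restart at a reduced dose without the joint best-interest agreement.

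**6. How often?** Section 1.4.4 (81 subjects, cutoff 21-Dec-2018, preliminary) reports related diarrhea in 34 subjects, none at Grade 3 to 4. For 0 of 81 the one-sided 95% upper limit is 1 − 0.05^(1/81) = 0.036, or 3.6%. For the non-hematologic row no bound can be derived: Grades 3 and 4 are mostly reported together, maximum medical management is not reported, and a related myocardial infarction in Section 1.5 has no grade. No related non-hematologic event is identified as Grade 4.

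**The case against.** The strongest reply is that the texts fit together. The bullet is specific to Grade 4 and the rows are general. A subject who continues under the bullet's exception needs hold-and-reduce steps, and the rows supply them. The separate stop rows for febrile neutropenia and QTcF concern events with no bullet of their own, so the lack of a Grade 4 non-hematologic row proves little. Section 4.5.3 points to the bullet for diarrhea.

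Most of this stands. It is the likely intent, and it makes this a clarification rather than a change of policy. It does not remove the inconsistency. Specificity cuts both ways, since the rows are narrower on causality and medical management. The rows also give hold as the initial action without saying that agreement must come first. If they did prevail, a drug-related Grade 4 event despite maximum management would get a softer default than a Grade 4 event outside the rows.

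A reader might infer that sites may freely re-dose after Grade 4 toxicity. The documents do not support that: the safeguards in step 5 apply on either route.

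**Conclusion.** The inconsistency is real and narrow. For a drug-related Grade 4 non-hematologic AE on maximum medical management, or uncontrolled Grade 4 diarrhea, the bullet's default is to stop and the table's is to hold and then reduce, with no stated priority. The practical consequence is mainly a possible reduced-dose restart without the joint best-interest agreement.

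Few subjects are likely to be affected. The 3.6% limit for diarrhea covers Grades 3 and 4 together, pooled over all Part 1 doses and schedules; applying it to the Part 2 regimen is an assumption. The frequency for the non-hematologic row is unknown.

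A reader might also infer that dose-finding or the safety analysis is compromised. It is not. DLTs are defined in Section 4.5.1 independently of what follows the event, so escalation and MTD decisions do not change. Any effect on AEs leading to discontinuation (SAP Section 7.6.3) is on a descriptive tabulation in a study with no formal hypothesis (Protocol Section 1.2).

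**What to change.** Limit the two rows of Table 4.5.2-1 to Grade 3, keeping their qualifiers, and add one row for Grade 4 non-hematologic AEs, diarrhea included: discontinue BMS-986158 unless the sponsor's medical monitor and the investigators agree that continuing serves the subject's best interest; if continued, hold to baseline or Grade 1 and then follow the Grade 3 row.

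A shorter alternative is one sentence in Section 4.5.2 saying that the Grade 4 bullet prevails over Table 4.5.2-1.

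Either way the cost is a wording amendment. It adopts the default and exception already in the bullet and adds no visits, data or analyses.

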4.5.3 Management of Diarrhea for BMS-986158

For symptoms of diarrhea that occur at any time during treatment with BMS-986158, dose interruption is recommended until diarrhea resolves. After recovery, dose reduction or discontinuation should follow the criteria in Section 4.5.2 depending on the severity of the diarrhea. The following are guidelines for the management of diarrhea and are not intended to replace the clinical judgment of the treating physician(s):

For Grade 3 or higher events of diarrhea that are not controlled (ie, to Grade 1 or baseline) with loperamide or lomotil, dosing of BMS-986158 should be interrupted, as continued dosing will likely result in increased severity of diarrhea. In addition, evaluation of infectious causes should be considered. After recovery, dose reduction or discontinuation should follow the criteria in the protocol, depending on the severity of the diarrhea. The following are guidelines for the management of diarrhea, and should be used along with the clinical judgment of the treating physician(s).

- Diet: Recommendations should include eating small, frequent meals, diet modification (avoiding milk products, spicy and/or fatty foods, alcohol, and caffeine), and aggressive oral hydration.
- Treatment with Loperamide: Loperamide should be started at the earliest sign of (1) a poorly formed or loose stool, (2) the occurrence of 1 to 2 more bowel movements than usual in 1 day, or (3) an increase in stool volume or liquidity. Loperamide may be taken in the following manner: 4 mg at the first onset of diarrhea, then 2 mg every 2 hours around the clock until diarrhea-free for at least 12 hours. Subjects may take loperamide 4 mg every 4 hours during the night. This dose regimen is higher than the standard dose of loperamide but is typical for the treatment of diarrhea caused by anticancer therapy. Subjects should be provided with loperamide and instructed in its use at the initial treatment visit so that they have sufficient supply on hand in case antidiarrheal support is required. It is important that loperamide is taken as instructed. For subjects who cannot tolerate loperamide or who do not get adequate relief with maximum doses, standard doses of Lomotil® (diphenoxylate/atropine) may be added or used instead of loperamide.
- Additional antidiarrheal measures, such as octreotide, may be used at the discretion of the investigator or treating physician.
- Increase Fluid Intake and, if applicable, consider stopping anti-hypertensive therapy and nonsteroidal anti-inflammatory drugs (NSAIDs): Hypotension and/or renal insufficiency can occur in the setting of volume depletion from severe diarrhea. At the onset of any diarrhea, subjects should be instructed to increase fluid intake to help maintain fluid and electrolyte balance during episodes of diarrhea. Parenteral hydration should be started if oral hydration is not sufficient. The investigator should consider interrupting anti-hypertensive therapy and NSAIDs, if medically appropriate.

4.5.4 Management Algorithms for Immuno-oncology Agents

Immuno-oncology agents are associated with AEs that can differ in severity and duration from AEs caused by other therapeutic classes. Nivolumab is considered an immuno-oncology agent in this protocol. Early recognition and management of AEs associated with immuno-oncology agents

may mitigate severe toxicity. Management algorithms have been developed form extensive experience with nivolumab and ipilimumab to assist investigators in assessing and managing the following groups of AEs:

- Gastrointestinal
- Renal
- Pulmonary
- Hepatic
- Endocrinopathies
- Skin
- Neurological

The clinical nature of AEs noted with nivolumab (in combination with BMS-986158) will determine the role of the above algorithms for use in toxicities related to its use in this study. The algorithms recommended for utilization in this protocol are included in Appendix 10.

In addition, nivolumab therapy can be associated with visual complaints. Inflammation of components within the eye is an uncommon, but clinically important, event. An ophthalmologist should evaluate visual complaints with examination of the conjunctiva, anterior and posterior chambers, and retina. Topical corticosteroids may be used to manage low-grade events. Low-grade events that do not resolve and high-grade events should be managed with systemic corticosteroids. Consultation with a BMS Medical Monitor should be sought for all cases of ocular inflammatory events. Complaints of double vision should also prompt medical evaluation.

Cases of rare events, some with fatal outcome, have been reported with nivolumab (see the Investigator Brochure for Nivolumab for details). If a participant develops signs and symptoms of myositis, myocarditis or rhabdomyolysis or other rare event, the case should be discussed with BMS Medical Monitor, close monitoring should be implemented, and the patient referred to a specialist for assessment and treatment without delay. Based on the severity of the event, nivolumab should be withheld or discontinued, and appropriate treatment instituted. For Grade 3 myocarditis, nivolumab should be permanently discontinued.

4.6 Blinding/Unblinding

This study is a non-randomized open-label study for Part 1 and Part 2. Interactive Response Technology (IRT) will be used in Part 2 for treatment assignment. Data emerging from this exploratory study may be necessary to inform timely decisions for adjusting procedures in subsequent portions of the study, including early termination of the study. Additionally, availability of the open label treatment assignments may facilitate optimization of the bioanalytical analysis of samples.

4.7 Treatment Compliance

At scheduled PK sample collections laboratory evaluation days, BMS-986158 will be administered to the subject in the clinical facility. At all other times throughout the study, BMS-986158 will be

administered on an outpatient basis. The investigator and the study personnel will ensure that each subject receives the calculated dose of the study drug. Treatment compliance will be monitored by drug accountability, as well as recording BMS-986158 administration in subjects' medical records and CRF. Subjects must keep a diary of study medication doses and any missed doses (see Section 4). Subjects should bring all drug containers to each study visit for drug reconciliation. Drug supplies will be inventoried and accounted for throughout the study. The Drug Accountability Log will be reviewed by the study monitor during site visits and at the completion of the study. Any discrepancy should be brought to the attention of the Sponsor.

